7.5.3 Optimal Biological Dose Selection

At the completion of the trial, when all patients have been followed up fully and all outcomes evaluated, the optimum biological dose (OBD) will be defined as the dose maximizing the sample mean percentage of WBCs that are T-cells, evaluated at one year of follow up.

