1.0 Objectives

Primary Objective:

- To determine the safety and establish the optimal biologic dose of CYT107.

Secondary objectives:

- To determine the rate of cytomegalovirus (CMV), Epstein-Barr virus (EBV) and BK viral infections in umbilical cord blood stem cell transplantation (CBT) and haploidentical stem cell transplantation (haplo-SCT) patients who receive three doses of IL-7 following engraftment.
- To calculate the OS, PFS and, cumulative incidence of GVHD and cumulative incidence of relapse
- To evaluate the effects of CYT107 on the recovery of T, NK and B cell populations and their functions in vitro; these data will be used to identify the optimal dose to move to a phase II trial.

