7.0 Statistical Considerations

7.1 Outcomes and Covariates

7.1.1 Primary Outcomes

Toxicity. Dose limiting toxicity (DLT) is defined as any of the following events: grade 3 or 4 GVHD, secondary graft failure, disease relapse, development of PTLD, development of PML, grade 2 organ failure or grade 2-4 skin rash, fatigue, AST and ALT elevations, allergic anaphylaxis, or hemolytic anemia, attributable to CYT107, or death, occurring within 42 days of the first CYT107 injection.

Biological Responses. The absolute number and percentage of total White Blood Cells (WBCs) consisting of T-cells and of B-cells will be observed at 1, 3, 6, 9 and 12 months.

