7.3.2 Within-Dose Safety Monitoring Rule

For each dose $d = 1, 2, 3$, denote $p(d) = \Pr(\text{DLT at dose } d)$. Assume that each $p(d)$ follows a beta(.35, .65) prior. Applying the method of Thall et al.⁴¹, enrollment to dose d will be stopped if $\Pr[p(d) > .35 | \text{data}] > .85$. This criterion will be applied continuously starting at $n = 3$, which implies that accrual to d should be stopped if [number of DLTs] / [number of patients evaluated] is greater than or equal to 3/3 or 4/5. To apply this safety rule for each dose to 2 cohorts of size 3 each may or may not require suspension of accrual. For each dose (a) once 1 or more pats in cohort 1 (pats #1,2,3) have “No toxicity” by day 42 of followup, cohort 2 may begin enrollment, and (b) once 2 or more pats in cohorts 1 and 2 combined (pats #1,2,3,4,5,6) have “No toxicity” by day 42 of follow up, the last patient 7 may be enrolled. This rule has the following operating characteristics.

Operating characteristics of the within-dose safety monitoring rule

True $p(\text{DLT} d)$	$\Pr(\text{Stop accrual to } d)$	Sample Size	Quartiles
.35	.163	7, 7, 7	
.55	.497	4, 7, 7	
.60	.601	4, 6, 7	
.65	.607	3, 4, 7	

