7.4 Enrichment

If enrollment to a dose d is stopped early at $n(d) = 3$ or 6 before 7 patients are treated, then the remaining $7 - n(d) = 1$ or 4 patients will be randomized between the remaining two doses. If enrollment to 2 doses is stopped early, then all remaining patients, up to $N_{\text{max}} = 21$, will be treated at the one remaining dose. If enrollment to all 3 doses is stopped early, then the trial will be stopped with no dose selected.

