7.7 Summary Reports

The investigator is responsible for completing a toxicity summary report and submitting it to the IND Office, Medical Affairs and Safety Group, for review and approval. This should be submitted after the first, the first three, and the first five evaluable patients per cohort, have completed 42 days post-first CYT107 injection.

A copy of the cohort summary should be placed in the Investigator's Regulatory Binder, under "Sponsor Correspondence".

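### The optimal biological dose is chosen on one-year T-cell percentage alone, so a dose that first meets the plan's own DLT criterion at its seventh patient (4/7) remains selectable

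*Combined protocol and SAP*

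**What the plan says.** Section 1.0 gives the primary objective as "To determine the safety and establish the optimal biologic dose of CYT107". Section 7.1.1 lists toxicity first among the primary outcomes ("Dose limiting toxicity (DLT) is defined as any of the following events", followed by the list).

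Three sections then bear on which dose is named:

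- **Section 7.3.2** gives each dose a beta(.35, .65) prior on its DLT probability p(d). It says that "enrollment to dose d will be stopped if" Pr[p(d) > .35 | data] exceeds .85, checked continuously from n = 3. Enrollment is the only thing the criterion acts on. Once at least two of the first six patients are free of toxicity at day 42, "the last patient 7 may be enrolled".
- **Section 7.4** deals with a dose stopped at n(d) = 3 "or 6 before 7 patients are treated, then the remaining" places are randomized to the other doses. On selection it says only this: "If enrollment to all 3 doses is stopped early, then the trial will be stopped with no dose selected".
- **Section 7.5.3** states that "the optimum biological dose (OBD) will be defined as the dose maximizing the sample mean percentage of WBCs that are T-cells" at one year. It mentions neither DLTs nor a set of eligible doses.

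Section 7.5.1 tabulates the primary variables by dose. Section 7.7 asks for toxicity summaries "after the first, the first three, and the first five evaluable patients per cohort". Neither is a selection rule.

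**The concern.** The plan has one formal safety threshold, and it does not enter the rule that produces the trial's main conclusion. Two situations are left open.

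The first is a dose closed early while at least one other dose stays open. Section 7.4 makes sense only if closed doses cannot be selected, but it does not say so when one or two doses close.

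The second matters more: a dose that passes every look through n = 6 and meets the criterion when its seventh patient is evaluated. If no other dose has closed, all places are filled and stopping enrollment changes nothing. If enrichment is under way, further accrual to the dose would stop, but its eligibility for selection is still not stated.

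Read literally, the plan can therefore name as optimal a dose that its own criterion rates as too toxic. Section 7.3.1 adds weight to this. It says that neither toxicity nor biological response need rise with dose, so the T-cell maximum cannot be presumed to fall on a tolerable dose.

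**Working it through.** **Inputs (Sections 7.3.1 and 7.3.2).** Prior beta(.35, .65); criterion Pr[p > .35 | data] > .85; looks from n = 3; 7 patients per dose. After x DLTs in n patients the posterior is beta(.35 + x, .65 + n − x).

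**Step 1: which counts meet the criterion.**

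| n | smallest x that meets it | Pr[p > .35] | next lower x |
|---|---|---|---|
| 3 | 3 | .985 | 2/3: .834 |
| 4 | 3 | .932 | 2/4: .694 |
| 5 | 4 | .973 | 3/5: .8485 |
| 6 | 4 | .929 | 3/6: .746 |
| 7 | 4 | .865 | 3/7: .637 |

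This agrees with the printed boundary of 3/3 or 4/5, read as the sample size at which each count first applies.

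**Step 2: reproduce the plan's table.** Write q = 1 − p. Counting the paths that cross at n = 3, 4 and 6 (none can first cross at n = 5), the probability of closing by n = 6 is

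c6 = p³ + 3p³q + 6p⁴q².

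Sixteen paths reach 3/6 without crossing. A DLT in patient 7 then gives 4/7, so

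P(first met at n = 7) = 16p⁴q³, and c7 = c6 + 16p⁴q³.

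At p = .35: c6 = .0429 + .0836 + .0380 = .1645; 16p⁴q³ = .0659; c7 = .2305 before rounding of the parts.

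| true p | printed | c6 (looks to n = 6) | c7 (looks to n = 7) |
|---|---|---|---|
| .35 | .163 | .165 | .230 |
| .55 | .497 | .502 | .636 |
| .60 | .601 | .600 | .732 |
| .65 | .607 | .694 | .817 |

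The first three rows match looks through n = 6 and not through n = 7. The printed table therefore does not count a crossing at n = 7. The .65 row fits neither column, and nothing here relies on it.

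**Step 3: size of the gap.** For one dose, 16p⁴q³. For the trial, the case in which stopping enrollment has no effect is that no dose closes by n = 6 and at least one first meets the criterion at n = 7. With three independent doses sharing p this is (1 − c6)³ − (1 − c7)³. At p = .35: .8355³ − .7695³ = .583 − .456 = .127.

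| true p | c6 | c7 | one dose first met at n = 7 | no closure, at least one first met at n = 7 |
|---|---|---|---|---|
| .20 | .033 | .046 | .013 | .036 |
| .35 | .165 | .230 | .066 | .127 |
| .50 | .406 | .531 | .125 | .106 |
| .65 | .694 | .817 | .122 | .022 |

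With true rates of .20, .35 and .50 on the three doses, the trial-level figure is the product of the three (1 − c6) terms minus the product of the three (1 − c7) terms: .480 − .344 = .136.

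These figures assume that each outcome is known before the next look. Section 7.3.2 lets patient 7 enter while earlier outcomes are pending, so a 4/6 result (.929) could emerge after the last place is filled. That would widen the gap.

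If the looks before n = 7 fall only at 3 and 6, the sizes named in Section 7.4, the per-dose figure at p = .35 is .078 instead of .066.

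**The case against.** The strongest case on the other side has four parts.

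**Closed doses are already covered.** Withholding selection when all three doses close makes sense only if a closed dose is ineligible. This largely stands: for early closures the text needs clarifying, not a new rule. It does not reach a dose that completes seven patients.

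**The criterion was written to stop accrual, and .865 is only just above .85.** The printed boundary does not list 4/7, and as a ratio 4/7 is below 4/5. Nor does the table show that n = 7 was meant as a decision point. All of this is fair, and using the criterion as a final filter does extend its role. But the formal rule is the posterior probability, with no upper limit on n, and three printed rows support reading the boundary as counts.

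**Nobody would choose a 4/7 dose, since DLTs are tabulated and toxicity summaries reviewed.** That is probably true in practice, but Section 7.5.3 defines the dose without leaving room for that judgement. If cohort in Section 7.7 means a dose group, no summary falls due at seven patients; that reading is uncertain and the point does not depend on it.

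**The gap can be overstated.** A reader might infer that a dose reaching 4/7 never has enrollment left to stop. That fails once another dose has closed and enrichment is running. With a common p, the chance that at least one of the other two doses closes by n = 6, 1 − (1 − c6)², is .302, .647 and .906 at p = .35, .50 and .65. A reader might likewise take 1 − (1 − .0659)³ = .185 at p = .35, or .330 and .324 at .50 and .65, as the chance that the stopping rule is powerless. Those figures include trials in which Section 7.4 would have triggered enrichment. Without those trials they become .127, .106 and .022.

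**Conclusion.** The omission is real and worth fixing before the final analysis. The selection rule has no DLT condition, and a dose that first meets the plan's criterion at 4/7 stays eligible whether or not enrichment is running.

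The per-dose chance is small at an acceptable DLT rate (.013 at p = .20), .066 at the .35 reference rate, and about one in eight at .50 and .65. The trial-level chance that this happens with no dose closed early peaks at .136 among the scenarios computed. The results rest on the plan's prior and threshold, looks at every n from 3, independent doses and outcomes known at each look.

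It would be natural to read these as the chance of naming too toxic a dose. The documents do not support that: such a dose must also have the highest mean T-cell percentage, and they give no distribution for that outcome.

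**What to change.** Reconcile Sections 7.3.2, 7.4 and 7.5.3 by adding to 7.5.3: *The OBD will be chosen only among doses that do not meet Pr[p(d) > .35 | data] > .85 on final data, including the seventh patient and any enrichment patients; if no dose qualifies, none is selected.*

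Beside the Section 7.3.2 operating characteristics, report the probability that a dose is excluded by n = 7: .046, .230, .531 and .817 at p = .20, .35, .50 and .65, against .033, .165, .406 and .694 by n = 6. These figures treat a dose closed early as excluded, with no outcomes pending.

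The sponsor should also state, consistently with Section 7.4, whether a dose that closes and then falls below the limit as pending outcomes arrive stays barred. An example is closure at 3/4 (.932) finishing at 3/6 (.746). That is a separate design choice, and the gap at n = 7 does not dictate the answer.

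The cost is a sentence or two and a few table entries, with no new data. The statistical price is a slightly higher chance of excluding an acceptable dose: .033 to .046 at p = .20.

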7.6 Trial Conduct

The Biostatistics Department Clinical Trial Conduct Website will be used to assign a dose to each patient at enrollment. This will be set up and overseen by a Research Statistician in the Biostat Dept to be designated by [name] prior to re-starting the trial at patient number 3, using a randomization sequence provided by [name]. The Principal Investigator and designated personnel in the SCT Dept will be responsible for recording all baseline covariates and outcome variables and implementing the within-dose stopping rule in terms of DLTs.

7.7 Summary Reports

The investigator is responsible for completing a toxicity summary report and submitting it to the IND Office, Medical Affairs and Safety Group, for review and approval. This should be submitted after the first, the first three, and the first five evaluable patients per cohort, have completed 42 days post-first CYT107 injection.

A copy of the cohort summary should be placed in the Investigator's Regulatory Binder, under "Sponsor Correspondence".

8.0 Criteria for Removal from the Study

Any patient can be removed from study for the following:

- Patient withdrawal of the informed consent
- Patient not being compliant
- An increasing or unexpected pattern of toxicity is observed deemed unacceptable by the study chairman
- Grade 2-4 skin rash, grade 3 or 4 GVHD, secondary graft failure, disease relapse, PTLD, PML or grade 3-4 non-hematological toxicity attributable to CYT107
- Disease progression
- Investigator judgment when the well-being and best interest of the patient is compromised
- Secondary Graft Failure
- 1 year after last injection.

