4.0 Treatment Plan and Study Design

CYT107 will not be administered before Day 60 but could be started as late as Day 180 post-CBT or haplo-SCT.

The active treatment period will be from the first injection of CYT107 and for 30 days after the last injection. The follow-up period will be for three years after the last injection.

Patients will be treated with CYT107 by intramuscular route (I.M.)* post CBT or haplo-SCT (from 60 to 180 days), with 1 of 3 doses below:

- 5 mcg/kg/dose for 3 doses, one week apart
- 10 mcg/kg/dose for 3 doses, one week apart
- 20 mcg/kg/dose for 3 doses, one week apart

Enrollment of the first 3 participants will be staggered by 14 days. Accrual in between cohorts will be halted for 30 days after the last patient in each cohort has received the last dose of CYT107.

* If the patient's platelet count is below 35,000, the product may be administered by subcutaneous route.

All patients will receive foscarnet for the management of CMV infection as per Stem Cell Transplantation and Cellular Therapy Department's standard of care.

Dose modifications

Treatment will be permanently discontinued for patients developing grade 3 or 4 GVHD, secondary graft failure, disease relapse, PTLD, PML, grade 2-4 skin rash, or grade 3-4 non-hematological toxicity attributable to CYT107.

Patients who develop grade 2 non-hematological toxicity attributable to the CYT107 will have the next dose withheld until the toxicity resolves to grade 1. If the toxicity resolves within 2 weeks the drug will be administered at the same dose, however if the toxicity takes more than 2 weeks to resolve the drug will be administered at the next lower level, or permanently discontinued if the patient was already at the lowest level. If the toxicity takes more than 4 weeks to improve to grade 1, the CYT107 will be permanently discontinued

For patients who at study entry have grade 0, 1 or 2 hematological toxicity and develop grade IV hematological toxicity attributable to the CYT107 will have the next dose withheld until the toxicity resolves to grade 2. If the toxicity resolves within 2 weeks the drug will be administered at the same dose, however if the toxicity takes more than 2 weeks to resolve the drug will be administered at the next lower level, or permanently discontinued if the patient was already at the lowest level. If the toxicity takes more than 4 weeks to improve to grade 2, the CYT107 will be permanently discontinued

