7.5 Data Analysis

7.5.1 Tabulation

Each primary and secondary variable will be tabulated by dose using summary statistics, consisting of counts and percentages for categorical variables and the sample median and range for numerical valued variables. Kaplan-Meier plots³⁴ will be used to estimate the PFS and OS distribution for each dose.

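### Section 8 lets patients be removed from the study for prognostic events and provides no outcome follow-up afterwards, so overall survival and the one-year T-cell comparison are at risk of bias

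*Combined protocol and SAP*

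**What the plan says.** **Removal from the study.** Section 8.0 begins "Any patient can be removed from study for the following". Its list includes "Grade 2-4 skin rash, grade 3 or 4 GVHD, secondary graft failure, disease relapse, PTLD, PML or grade 3-4 non-hematological toxicity attributable to CYT107", then disease progression, and ends with "1 year after last injection". The last item is an end-of-study criterion, so the list cannot be read as treatment discontinuation under another name.

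**Stopping treatment.** Section 4.0 has its own rule: "Treatment will be permanently discontinued for patients developing grade 3 or 4 GVHD, secondary graft failure, disease relapse, PTLD, PML, grade 2-4 skin rash", followed by attributable grade 3-4 non-hematological toxicity. It also states "The follow-up period will be for three years after the last injection".

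**Analyses that need the follow-up.** Section 7.5.1 says Kaplan-Meier plots "will be used to estimate the PFS and OS distribution for each dose" and gives no censoring rule. Section 7.1.2 measures time-to-event outcomes from CYT107 administration and asks for at least 12 months. Section 7.5.3 picks the optimal biological dose (OBD) by the sample mean percentage of white cells that are T-cells at one year, "when all patients have been followed up fully and all outcomes evaluated". Section 1.0 also lists the cumulative incidences of GVHD and relapse as objectives.

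**After removal.** Section 9.0 says that an adverse event still open when a patient goes off study is followed to resolution or stabilization. It also requires late serious events related to treatment to be reported. It does not mention vital status, relapse, GVHD or T-cell counts after removal.

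**The concern.** Most of these events mark patients whose prognosis has worsened. Kaplan-Meier assumes that a patient censored at a given time has the same later death risk as those still followed. A patient who leaves at relapse or with severe GVHD would be expected to have a higher risk, so censoring there would push estimated survival upward.

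The same removals affect three other quantities:

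- **OBD choice.** This belongs to the primary objective and rests on a raw mean of about 7 patients per dose. Removing 2 of 7 loses 29% of an arm (2/7 = 0.286). Several triggers are toxicities or GVHD that may vary with dose, so the loss may differ between arms. That would weaken the unbiased dose comparison that Section 7.3.1 gives as a reason for randomizing.
- **Relapse and GVHD incidence.** A patient removed for rash or toxicity is no longer observed for later relapse or GVHD.
- **PFS.** Removal at relapse does no harm, because relapse is already an event. Removal for GVHD, graft failure or toxicity could matter.

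**Working it through.** The plan states no survival target, dropout rate or censoring rule, so there is no figure to reproduce. The check sets the sections side by side and then illustrates the possible size.

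**Step 1: the two lists.** Rash, GVHD, graft failure, relapse, PTLD, PML and attributable grade 3-4 non-hematological toxicity appear, with the same grades, in both Section 4.0 and Section 8.0. Disease progression and the one-year limit appear only in Section 8.0. The same events therefore end treatment and may also end study participation.

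**Step 2: duration.** Section 4.0 gives three years after the last injection; Section 8.0 gives one year. The two conflict for every patient.

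**Step 3: simple bound on OS.** Inputs are the 3-year figures of the center's double cord blood series in Section 2.3, used for illustration only: OS 37% with non-relapse mortality (NRM) 42% when the day-30 lymphocyte count is above 150 × 10⁶/L, and OS 25% with NRM 59% at or below it.

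- Deaths after relapse = 1 − OS − NRM: 1 − 0.37 − 0.42 = 0.21; 1 − 0.25 − 0.59 = 0.16.
- With proportional cause-specific hazards and every death after relapse lost, apparent OS = OS^(NRM/(1 − OS)).
- Higher count: 0.37^(0.42/0.63) = 0.515. Lower count: 0.25^(0.59/0.75) = 0.336.
- At one year with constant hazards, true OS is 0.37^(1/3) = 0.718 and 0.25^(1/3) = 0.630. Apparent OS is 0.515^(1/3) = 0.802 and 0.336^(1/3) = 0.695.
- With half of those deaths lost, the exponent uses NRM + 0.5 × the relapse deaths. One-year OS reads 0.759 and 0.662.

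**Step 4: delay between relapse and death.** Step 3 places the death at the moment of relapse. A constant-hazard illness-death model removes that simplification. Let λN be the hazard of death without relapse, λR that of relapse, λP that of death after relapse (ln 2 / median, with an assumed median of 4 to 12 months), and a = λN + λR. Then:

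- NRM(t) = (λN/a)(1 − e^(−at))
- OS(t) = e^(−at) + λR(e^(−λP·t) − e^(−at))/(a − λP)
- Kaplan-Meier with every relapsed patient censored at relapse = e^(−λN·t)

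Solving for λR and λN at 3 years gives:

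| 3-year OS, NRM | Median after relapse | λR | λN | 3-year apparent OS | 1-year true → apparent |
|---|---|---|---|---|---|
| 37%, 42% | 4 months | 0.128 | 0.228 | 50.5% | 74.4% → 79.6% |
| 37%, 42% | 12 months | 0.191 | 0.254 | 46.7% | 75.0% → 77.6% |
| 25%, 59% | 4 months | 0.111 | 0.373 | 32.7% | 65.0% → 68.9% |
| 25%, 59% | 12 months | 0.164 | 0.414 | 28.9% | 64.8% → 66.1% |

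**Step 5: other relapse rates.** These inputs are assumptions that the documents do not give: a relapse hazard equivalent to 15% to 40% at one year, a non-relapse death hazard of 0.2 per year, and median survival after relapse of 4 to 12 months. In simulation, one-year OS is overstated by about 3 to 19 points if all relapsed patients are censored, 1 to 8 points if half are, and not at all if vital status is followed.

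Nothing comparable can be computed for GVHD, graft failure, rash or toxicity, because the documents give no death risk after those events.

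**The case against.** The strongest reply is that the plan never says survival is censored at removal. Removal is optional. Section 4.0 sets three years of follow-up without exempting patients who stop treatment, Section 7.1.2 asks for at least 12 months, and Section 7.5.3 presumes complete follow-up. A reader might infer that overall survival in this trial is informatively censored and biased upward as a matter of fact, or that Section 8.0 replaces treatment discontinuation. The documents support neither. Nor do they make all GVHD or all toxicity a ground for removal; the grades and the attribution are specified.

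It can also be said that the consequence for survival is modest. OS is secondary and descriptive, with no test. With 7 patients its one-year standard error is about √(0.718 × 0.282/7) = 17 points or √(0.63 × 0.37/7) = 18 points, larger than the one-year biases in Steps 3 and 4. On the OBD, patients who die before one year are missing from the mean whatever Section 8.0 says, and relapse can itself change the white-cell denominator.

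All of this limits the finding without removing it. Discretion is no safeguard, because case-by-case removal can itself depend on prognosis. The passages that imply full follow-up conflict with Section 8.0, at least on one year against three. Reporting of late treatment-related serious events would not capture deaths from relapse. Two analysts could follow this text and report different survival curves and a different OBD.

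**Conclusion.** The point holds as a conflict in the plan that carries a risk of bias; an established bias has not been shown. Section 8.0 permits removal from the study, in addition to stopping treatment, for events that predict outcome, and outcome follow-up after removal is not provided. If removal ends that follow-up, OS tends to be overstated, later relapse and GVHD go unobserved, and the one-year T-cell mean omits patients in a way that may differ by dose. The effect on the OBD is the more important one, because it bears on the primary objective, but its size cannot be computed from the documents.

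For OS, 51.5% against 37% and 33.6% against 25% at 3 years are worst-case illustrations. They assume that every death after relapse is lost and proportional hazards apply. They also come from a double cord blood series, whereas this trial admits several donor types and starts treatment at day 60 to 180. They should not be read as the expected error. On the same background rates, allowing for delay after relapse, the one-year error with full removal is about 1 to 5 points. It shrinks with partial removal and is zero if vital status is followed. This should be corrected, but it does not invalidate the design.

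**What to change.** - In Section 8.0, separate *off treatment* from *off study*. Leave the treatment-stopping criteria to Section 4.0 and reconcile the two lists without changing any clinical rule.
- State that vital status, relapse, GVHD and scheduled T-cell assessments continue in all treated patients after CYT107 stops, unless the patient withdraws consent for follow-up, dies or is lost.
- In Section 7.5.1, define censoring for OS and PFS, and state that OS is not censored when treatment stops.
- In Section 7.5.3, report how many patients per dose contribute to the one-year mean and why the others do not, and say how deaths before one year are handled.
- Reconcile the three-year follow-up in Section 4.0 with the one-year removal item in Section 8.0.

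The cost is a wording amendment and limited extra follow-up in at most 21 patients. One drawback remains: T-cell percentages measured after relapse need cautious interpretation and should be identified as such in the report.
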